3.1. Study Rationale

Tirzepatide is being developed for the treatment of type 2 diabetes mellitus (T2DM) as an adjunct to diet and exercise. In addition, it is being developed as a therapy for the indications of chronic weight management and nonalcoholic steatohepatitis.

Study I8F-MC-GPHX (GPHX) is being conducted to determine the disposition of radioactivity and pharmacokinetics (PK) of tirzepatide (LY3298176) in healthy male subjects following a single subcutaneous (SC) injection of approximately 4.1 mg tirzepatide containing approximately 100 μ Ci [14 C]-tirzepatide. The 100- μ Ci dose of the radiotracer will be administered to each subject to facilitate characterization of physiological disposition and metabolism of tirzepatide. The tirzepatide dose is therefore dependent upon the specific activity of the drug substance. At the target drug substance specific activity, the tirzepatide dose will be 4.1 mg. However, based on variability in the drug substance specific activity, the final tirzepatide dose will be approximately 4.1 mg and will be no higher than 5 mg.

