5.5. Justification for Dose

Based on data from a quantitative whole-body autoradiography disposition study for tirzepatide in male rats, a whole-body radiation dose in a 70-kg man following administration of a single SC 100- μCi (3.7-MBq) dose of [^{14}C]-tirzepatide was calculated to be 97.7 mrem (0.977 mSv). This effective radiation dose is defined as being within dose limits for members of the public (Category II study; World Health Organization, 1977) with a minor associated risk (risk Category IIa; International Commission on Radiological Protection [ICRP], 1992). Therefore, administration of a single SC 100- μCi (3.7-MBq) dose of [^{14}C]-tirzepatide would not be expected to represent a significant radiation exposure risk in man.

The specific activity of [^{14}C]-tirzepatide is approximately 20-24 $\mu\text{Ci}/\text{mg}$. A dose of tirzepatide that can provide a radioactive dose of 100 μCi per subject, is considered sufficient to facilitate characterization of the physiological disposition and metabolism of tirzepatide whilst complying with the “as low as (is) reasonably achievable” (ALARA) principle prescribed by the ICRP. Hence a tirzepatide dose of approximately 4.1 mg has been selected for this study.

Data from Phase 1 study GPGA has shown that a 5-mg dose of tirzepatide was well tolerated by healthy subjects and patients with T2DM, and is also planned as one of the doses to be

investigated in Phase 3 studies. Doses higher than 5 mg were achieved via escalation since a 5 mg dose was considered the MTD when administered as a single dose.

The study will be submitted for approval by the Administration of Radioactive Substances Advisory Committee.

6. Study Population

Eligibility of subjects for the study will be based on the results of screening medical history, physical examination, vital signs, clinical laboratory tests, and ECGs.

The nature of any conditions present at the time of the physical examination and any preexisting conditions will be documented.

Screening may occur up to 27 days prior to check-in. Subjects who are not enrolled within 27 days of screening may be subjected to an additional medical assessment and/or clinical measurements to confirm their eligibility.

Prospective approval of protocol deviations to recruitment and enrollment criteria, also known as protocol waivers or exemptions, are not permitted.

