9.5.4. Bioanalysis

Samples will be analyzed at a laboratory approved by the sponsor and stored at a facility designated by the sponsor.

Concentrations of tirzepatide will be assayed using a validated liquid chromatography tandem mass spectrometry method. Metabolite identification will be determined using appropriate techniques such as liquid chromatography (LC)/radiodetection and LC/mass spectroscopy.

Whole blood, plasma, expired air, urine, and fecal concentrations of radioactivity will be determined using liquid scintillation counting techniques. Whole blood and feces will be combusted prior to the liquid scintillation counting.

Bioanalytical samples collected during radiolabeled studies will be retained for a maximum of 2 years following last subject visit for the study. During this time, samples remaining after the bioanalyses may be used for exploratory analyses such as additional metabolism and/or protein binding work.

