6. TREATMENT

The study treatment will be a single dose of approximately 4.1-mg (approximately 100 μ Ci) [^{14}C]-tirzepatide. The treatment label presented in the TFLs will be ‘X.X mg [^{14}C]-tirzepatide’, where the TFLs will show the actual dosage level administered.

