9.3 Pharmacokinetic Assessment

9.3.1 Pharmacokinetic Analysis

The PK parameter estimates will be determined using non-compartmental methods in validated software program, Phoenix WinNonlin (Certara, Version 8.1 or later):

Plasma concentrations of tirzepatide (LY3298176) will be used to determine the following PK parameters, when possible:

Parameter	Units	Definition
AUC(0-∞)	ng.h/mL	area under the concentration versus time curve from time zero to infinity
AUC(0-t _{last})	ng.h/mL	area under the concentration versus time curve from time zero to time t, where t is the last time point with a measurable concentration
%AUC(t _{last} -∞)	%	percentage of AUC that is due to extrapolation from the last measurable concentration to infinity
C _{max}	ng/mL	maximum observed drug concentration
t _{max}	h	time of maximum observed drug concentration
t _{1/2}	h	half-life associated with the terminal rate constant (λ_z) in non-compartmental analysis
CL/F	L/h	apparent total body clearance of drug calculated after extra-vascular administration
V _{ss} /F	L	apparent volume of distribution at steady state after extra-vascular administration
V _z /F	L	apparent volume of distribution during the terminal phase after extra-vascular administration

The following pharmacokinetic parameters will be calculated for total radioactivity in plasma and whole blood:

Parameter	Units	Definition
AUC(0-∞)	ng equiv.h/mL	area under the concentration versus time curve from time zero to infinity
AUC(0-t _{last})	ng equiv.h/mL	area under the concentration versus time curve from time zero to time t, where t is the last time point with a measurable concentration
%AUC(t _{last} -∞)	%	percentage of AUC that is due to extrapolation from the last measurable concentration to infinity
C _{max}	ng equiv/mL	maximum observed drug concentration
t _{max}	h	time of maximum observed drug concentration
t _{1/2}	h	half-life associated with the terminal rate constant (λ_z) in non-compartmental analysis

Additional pharmacokinetic parameters may be calculated where appropriate.

The software and version used for the final analysis will be specified in the clinical study report. Any exceptions or special handling of data will be clearly documented within the final study report.

Pharmacokinetic analysis will, where possible, be carried out using actual postdose times recorded in the raw data.

The ratio of total radioactivity in whole blood : plasma will be calculated for each time point.

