The ratio of plasma tirzepatide : plasma total radioactivity will be calculated for each time point.

The ratio of total radioactivity in whole blood : plasma will be calculated based upon C_{max}, AUC(0-t_{last}) and AUC(0-∞).

The ratio of plasma tirzepatide : plasma total radioactivity will be calculated based upon C_{max} , $AUC(0-t_{last})$ and $AUC(0-\infty)$.

The percentage and cumulative percentage of radiolabeled dose excreted in expired air may also be presented, if applicable.

Analysis of the total radioactivity in faeces, urine, expired air, plasma and whole blood will be presented in a separate radioanalysis report. Cumulative recovery of total radioactivity in excreta will also be determined.

Formatting of tables, figures and abbreviations will follow the Eli Lilly Global PK/PD/TS Tool: NON-COMPARTMENTAL PHARMACOKINETIC STYLE GUIDE. The version of the tool effective at the time of PK analysis will be followed.

General PK Parameter Rules

- Actual sampling times will be used in the final analyses of individual PK parameters, except for non-bolus pre-dose sampling times which will be set to zero.
- C_{max} and t_{max} will be reported from observed values. If C_{max} occurs at more than one time point, t_{max} will be assigned to the first occurrence of C_{max} .
- Where concentration data are supplied in ng equiv/g a matrix density of 1g/mL will be used for pharmacokinetic calculation.
- AUC parameters will be calculated using a combination of the linear and logarithmic trapezoidal methods (linear-log trapezoidal rule). The linear trapezoidal method will be applied up to t_{max} and then the logarithmic trapezoidal method will be used after t_{max} . The minimum requirement for the calculation of AUC will be the inclusion of at least three consecutive plasma concentrations above the lower limit of quantification (LLOQ), with at least one of these concentrations following C_{max} .
- $AUC(0-\infty)$ values where the percentage of the total area extrapolated is more than 20% will be flagged. Any $AUC(0-\infty)$ value excluded from summary statistics will be noted in the footnote of the summary table. An alternative AUC measure, such as AUC to a common time point, may be calculated if $AUC(0-\infty)$ cannot be reliably calculated.

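### Must the SAP name the specific activity behind the ng-equivalent results and the mass dose behind CL/F?

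*SAP*

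**What the plan says.** **Measurement.** Protocol 9.5.4 separates the two assays. For parent drug: "Concentrations of tirzepatide will be assayed using a validated liquid chromatography tandem mass spectrometry method". Radioactivity in plasma and whole blood is measured by liquid scintillation counting.

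**Analysis.** SAP 9.3.1 reports tirzepatide in ng/mL and radioactivity in ng equiv/mL. It plans their ratio at each sampling time ("The ratio of plasma tirzepatide : plasma total radioactivity will be calculated for each time point") and again on Cmax, AUC(0-tlast) and AUC(0-∞). Its one conversion rule is "Where concentration data are supplied in ng equiv/g a matrix density of 1g/mL will be used for pharmacokinetic calculation". It plans CL/F ("apparent total body clearance of drug calculated after extra-vascular administration"), Vss/F and Vz/F without naming the dose. On sampling times it is explicit: "Pharmacokinetic analysis will, where possible, be carried out using actual postdose times recorded in the raw data". It also says that the analysis of total radioactivity will appear in a separate radioanalysis report.

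**Specific activity and dose.** Protocol 5.5 says the specific activity of labelled "tirzepatide is approximately 20-24" µCi/mg. Protocol 3.1 makes the mass dose depend on specific activity, caps it at 5 mg, and states: "At the target drug substance specific activity, the tirzepatide dose will be 4.1 mg". That target is not given as a number. Protocol 5.1 bases the recovery criterion on the actual dose. Protocol 7.1 keeps each syringe so that residual radioactivity can be measured. SAP 6 sets the treatment label, "where the TFLs will show the actual dosage level administered".

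**The concern.** Specific activity does not cancel in the parent:total ratio, because only the denominator is converted. The SAP fixes density, yet leaves open a factor that the protocol itself shows varying by about a fifth. Radioactivity AUC and Cmax are secondary endpoints, and their ng-equivalent values scale inversely with the specific activity used. The parent:total ratio shows how much of the circulating radioactivity is unchanged drug, so it informs the metabolism objective. CL/F and the volume terms scale directly with the mass dose entered. A wrong factor would shift all subjects dosed from one batch together, so it would not show up as between-subject scatter or as an outlier.

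**Working it through.** **Inputs.** Radioactive dose 100 µCi, specific activity (SA) about 20-24 µCi/mg (Protocol 5.5); mass dose 4.1 mg at target, at most 5 mg (Protocol 3.1). The batch value and the subjects' actual doses are not in the documents, so only a range can be shown.

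**1. The plan's own figure.** Mass dose = radioactive dose / SA.
- 100/24 = 4.17 mg. The stated 4.1 mg differs by 4.1/4.167 − 1 = −1.6%.
- 100/20 = 5.00 mg, exactly the cap.
- In reverse, 100/4.1 = 24.39 µCi/mg. A dose that rounds to 4.1 mg (4.05 to 4.15) gives 24.7 to 24.1.

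All these quantities are stated as approximate, so 24.4 against 20-24 is rounding, not a contradiction.

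**2. Effect of the wrong specific activity.** 1 nCi/mL = 1000/SA ng equiv/mL. If 24.39 is used, the relative error in ng equivalents is SA(true)/24.39 − 1, and the parent:total ratio is multiplied by 24.39/SA(true). The true ratio of 0.80 is an assumption for illustration; the documents give no expected value.

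| True SA (µCi/mg) | ng equiv per nCi | Error in ng equiv | Ratio multiplier | 0.80 reads |
|---|---|---|---|---|
| 24.39 | 41.0 | 0 | 1.000 | 0.80 |
| 24 | 41.7 | −1.6% | 1.016 | 0.81 |
| 22 | 45.5 | −9.8% | 1.109 | 0.89 |
| 20 | 50.0 | −18.0% | 1.220 | 0.98 |

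In the last row any true ratio above 20/24.39 = 0.82 would read above 1. In the opposite mistake (20 used, 24.39 true) the multiplier is 0.82 and 0.80 reads 0.66.

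**3. Effect of the wrong mass dose.** CL/F = mass dose / AUC(0-∞), and the volume terms scale in the same way. If 4.1 mg is entered:
- 4.17 mg given: −1.6%
- 4.55 mg given: 4.1/4.545 − 1 = −9.8%
- 5.00 mg given: 4.1/5.0 − 1 = −18.0%

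**4. What is not affected.** Percentage of radioactive dose recovered (both terms are activities), the whole blood:plasma ratio (the same factor in both terms), tmax and half-life.

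**5. Would the plan lead anyone to the wrong value?**
- *Conversion.* The density rule covers data that arrive already in ng equivalents per gram. On that wording the division by specific activity is done by the radioanalytical laboratory before the PK analyst receives the data, and density is the step that remains. A rule missing from SAP 9.3.1 is therefore not shown to be missing from the laboratory's own documents.
- *Batch value.* The mass dose is defined through specific activity and must stay within 5 mg while delivering about 100 µCi. The dose cannot be prepared to that specification without knowing the batch's specific activity. The figure 24.4 is printed nowhere; it comes only from dividing two approximate numbers.
- *Mass dose.* The recovery criterion, the syringe residuals and the table label all point to the actual dose. A 20 µCi/mg batch delivering 100 µCi would be labelled 5.0 mg under SAP 6, so a clearance computed from 4.1 mg would visibly disagree with its own table label.

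**The case for a change.** The best argument for a change is that it costs a few sentences. The SAP must be signed before the first subject visit, and a rule can be fixed then even if the batch value is not yet known. The documents specify actual values for sampling times, recovery and the label, but not for the clearance input. Nothing says that syringe residuals correct a subject's mass dose. The radioanalysis report may state the specific activity, but neither document says that it will.

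All of that is accurate, and a cross-reference would do no harm. It shows, however, that a sentence is absent, not that any stated rule gives a wrong result. The larger figures need someone to ignore the batch value and back-calculate one from rounded numbers. The results exposed are also limited. Protocol 10.3.2.1 makes CL/F and V/F optional, and the parent:total ratio is not an endpoint in Protocol Section 4. The metabolism endpoint there is the number of metabolites, which does not depend on the conversion factor. That leaves radioactivity AUC and Cmax, which are summarised descriptively with no formal inference. If a wrong factor were used, it would be one multiplier per batch, and the results could be rescaled without new samples.

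**Conclusion.** No change is needed. The omission is real and the arithmetic is right, but this is detail that the laboratory and the PK analyst would supply sensibly, not an error or a contradiction in the plan. The possible error is 1.6% if the batch is at 24 µCi/mg. It reaches 18% low for ng equivalents and 22% high for the parent:total ratio only if a 20 µCi/mg batch were converted with 24.4; CL/F and the volume terms would be 18% low if 4.1 mg were entered when 5.0 mg was given. Nothing in the documents suggests either would be done. The primary endpoint is untouched. The conclusion assumes that the radioanalytical laboratory converts with the specific activity of the batch administered and that CL/F uses the actual dose. Both fit the wording of the protocol and SAP, but neither can be confirmed without the radioanalysis report.

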- The pre-dose average concentration for single-dose data from non-endogenous compounds will be set to zero. Otherwise, only quantifiable concentrations will be used to calculate average concentrations.
- Concentrations at a sampling time exceeding the sampling time window specified in the protocol, or $\pm 10\%$, will be excluded from the average concentration profiles.

- Concentrations excluded from the mean calculation will be documented in the final study report.
- A concentration average will be plotted for a given sampling time only if 2/3 of the individual data at the time point have quantifiable measurements that are within the sampling time window specified in the protocol or $\pm 10\%$. An average concentration estimated with less than 2/3 but more than 3 data points may be displayed on the mean concentration plot if determined to be appropriate and will be documented within the final study report.

Treatment of Outliers during Pharmacokinetic Analysis

Application of this procedure to all PK analyses is not a requirement. Rather, this procedure provides justification for exclusion of data when scientifically appropriate. This procedure describes the methodology for identifying an individual value as an outlier for potential exclusion, but does not require that the value be excluded from analysis. The following methodology will not be used to exclude complete profiles from analysis.

Data within an Individual Profile

A value within an individual profile may be excluded from analysis if any of the following criteria are met:

- For PK profiles during single dosing of non-endogenous compounds, the concentration in a pre-dose sample is quantifiable.
- For any questionable datum that does not satisfy the above criteria, the profile will be evaluated and results reported with and without the suspected datum.

Data between Individual Profiles

1. If $n < 6$, then the dataset is too small to conduct a reliable range test. Data will be analyzed with and without the atypical value, and both sets of results will be reported.
2. If $n \geq 6$, then an objective outlier test will be used to compare the atypical value to other values included in that calculation:
 - a. Transform all values in the calculation to the logarithmic domain.
 - b. Find the most extreme value from the arithmetic mean of the log transformed values and exclude that value from the dataset.

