 - c. Calculate the lower and upper bounds of the range defined by the arithmetic mean $\pm 3*SD$ of the remaining log-transformed values.
 - d. If the extreme value is within the range of arithmetic mean $\pm 3*SD$, then it is not an outlier and will be retained in the dataset.

- e. If the extreme value is outside the range of arithmetic mean $\pm 3*SD$, then it is an outlier and will be excluded from analysis.

If the remaining dataset contains another atypical datum suspected to be an outlier and $n \geq 6$ following the exclusion, then repeat step 2 above. This evaluation may be repeated as many times as necessary, excluding only one suspected outlier in each iteration, until all data remaining in the dataset fall within the range of arithmetic mean $\pm 3*SD$ of the log-transformed values.

Reporting of Excluded Values

Individual values excluded as outliers will be documented in the final report. Approval of the final report will connote approval of the exclusion.

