9.3.2 Pharmacokinetic Statistical Methodology

No formal statistical analysis will be performed for this study.

PK parameters and concentrations for tirzepatide and total radioactivity in plasma and whole blood will be summarized and listed.

Ratios of PK concentrations (plasma tirzepatide to plasma total radioactivity and total whole blood radioactivity to plasma total radioactivity) and parameters will summarized and listed.

Plasma concentrations of tirzepatide and total radioactivity in plasma and whole blood will be graphically represented with an arithmetic mean plot and a concentration-time profile by subject.

Expired air data will be listed (if radioactivity is detected).

The percentage of radiolabeled dose excreted in feces, urine and expired air will be determined by the radioanalytical lab and reported in the radioanalysis report. Cumulative recovery of total radioactivity in excreta will also be determined.

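### If run and followed, the PK outlier test for six or more values drops a valid value from 25% to 31% of clean datasets, and it lacks the with/without reporting required below six

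*SAP*

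**What the plan says.** The rules are in SAP 9.3.1, under the heading on treatment of outliers.

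- **Preamble.** The procedure need not be applied to every PK analysis. It identifies candidates for exclusion "but does not require that the value be excluded from analysis". It is confined to individual values: "The following methodology will not be used to exclude complete profiles from analysis".
- **Within one profile.** For a questionable datum other than a quantifiable predose sample, "the profile will be evaluated and results reported with and without the suspected datum".
- **Between profiles, n < 6.** The SAP says "then the dataset is too small to conduct a reliable range test", and continues: "Data will be analyzed with and without the atypical value, and both sets of results will be reported".
- **Between profiles, n ≥ 6.** Values are logged, the one furthest from the mean is removed, and limits of mean ± 3 SD are computed from the rest. If the removed value is outside the limits, "then it is an outlier and will be excluded from analysis". The step may be repeated while at least six values remain.
- **Reporting.** "Individual values excluded as outliers will be documented in the final report". A second summary is not required in the n ≥ 6 branch.

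SAP 9.3.2 adds: "PK parameters and concentrations for tirzepatide and total radioactivity in plasma and whole blood will be summarized and listed". SAP section 7 and protocol section 5.2 cap enrolment at eight, with up to six dosed initially and at least four to complete. In between-subject summaries the n ≥ 6 branch can therefore operate only at n = 6, 7 or 8.

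**The concern.** A 3 SD limit sounds strict, but that impression belongs to a known SD, or one estimated from many values. Here the SD comes from five to seven values after the furthest has been taken away, so it is small and unstable. The value tested against it is always the most extreme one. The limit will be crossed often in data with nothing wrong in them.

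Two faults of wording add to this. Step 2e makes exclusion automatic, while the preamble says it is not required. And the safeguard of reporting both ways stops at n = 6, one value above the size the SAP itself regards as too small for a range test.

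A genuine Cmax, AUC or concentration could then be left out of its summary with no dosing, sampling or assay error behind it. In a study of this size, the spread across subjects is much of what the PK summary conveys, and it is the spread that exclusion shrinks. No rule says when a value counts as atypical, so the decision to test is made after the data are seen.

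**Working it through.** The SAP states no error rate for this test, so there is no figure of its own to reproduce.

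**Inputs.** n = 6, 7 or 8 (SAP section 7); limits of 3 SD from the remaining n − 1 log values (SAP 9.3.1); log-normal AUC and Cmax (SAP 9.1). *Clean* data are independent normal values on the log scale.

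**Exclusion rate.** For one value named in advance, its distance from the mean of the others, divided by their SD and by √(1 + 1/(n−1)), follows a t distribution with n − 2 degrees of freedom. The chance that it falls outside the limits is P = Pr(|t| > 3/√(1 + 1/(n−1))). The most extreme of n values is the one tested, so the rate per dataset is n × P.

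| n | t limit | df | P | n × P | Simulated |
|---|---|---|---|---|---|
| 6 | 3/√1.2000 = 2.74 | 4 | 0.0520 | 31.2% | 31.2% |
| 7 | 3/√1.1667 = 2.78 | 5 | 0.0390 | 27.3% | 27.3% |
| 8 | 3/√1.1429 = 2.81 | 6 | 0.0309 | 24.7% | 24.7% |

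The last column applies the SAP steps to 1,000,000 simulated datasets per n, with a single exclusion. For comparison, a limit at 3 true SDs would be crossed by at least one of n clean values with probability 1 − (1 − 0.0027)^n, which is 1.6% at n = 6 and 2.1% at n = 8.

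**Effect on spread** (mean log-scale SD in units of the true SD, same simulation).

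| n | When fired: before → after | Fall | All datasets: before → after | Fall |
|---|---|---|---|---|
| 6 | 0.952 → 0.507 | 47% | 0.951 → 0.812 | 14.6% |
| 7 | 0.959 → 0.554 | 42% | 0.959 → 0.849 | 11.5% |
| 8 | 0.966 → 0.593 | 39% | 0.965 → 0.873 | 9.5% |

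The datasets in which the test fires were no more dispersed than the rest (0.952 against 0.951 at n = 6). The exclusion therefore biases the spread downward and corrects nothing.

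**On the reported scale.** The documents give no CV. Assuming a true CV of 30% and n = 6, when the test fires the median geometric CV falls from 27.9% to 14.5%, the geometric mean shifts by a median of about 10%, and the excluded value is typically 1.8-fold from the rest.

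**If only odd-looking values are tested.** The SAP gives no trigger. Suppose a value is queried only if it is at least 2-fold from the geometric mean of the others (assumed; n = 6).

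| Assumed CV | Clean datasets queried | Queried and excluded |
|---|---|---|
| 20% | 0.8% | 0.7% |
| 30% | 16.5% | 9.3% |
| 40% | 44.1% | 19.2% |
| 50% | 65.6% | 24.8% |

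At CV 30% the test supports excluding 9.3/16.5 = 56% of the valid values put to it. With a higher trigger at CV 30%, the share losing a value is 1.9% at 2.5-fold and 0.3% at 3-fold.

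**Shape of the data.** If log values follow a t distribution with 5 df, the exclusion rates for n = 6, 7 and 8 are 39%, 37% and 36%. If they are uniform, the rates are 23%, 17% and 13%.

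**The case against.** The strongest reply is that 25% to 31% describes a procedure run on every dataset, which the SAP does not ask for. Step 2 starts from a value already thought atypical, the preamble makes use optional, and a demanding analyst would test few clean datasets: with a 3-fold trigger and a CV of 30%, only 0.3% would lose a value. The branch may not be reached either, since up to six are dosed, four completers suffice, and below six values both sets of results are already required. The harm is bounded: whole profiles cannot be dropped, exclusions are documented, individual values are listed, and with at most eight subjects a reader can recompute either summary. Nothing inferential depends on it. The SAP also does not forbid showing the untrimmed summary, and the table shells, which are not available here, might include it.

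Most of this stands as a limit on reach. The headline rate is conditional, and the rate in practice could be anywhere from near zero to about 25% under the triggers and CVs examined. It does not rescue the test. The SAP presents the procedure as an objective basis for excluding data, and at these sizes it often endorses removing values that are valid. Optional use also conflicts with the wording of step 2e, and nothing in the SAP text requires the untrimmed summary for n ≥ 6.

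**Conclusion.** The concern holds. Under independent log-normal data, and if the test is run and step 2e followed, a valid value is lost in 31.2%, 27.3% and 24.7% of clean datasets at n = 6, 7 and 8. Each exclusion cuts the log-scale SD by 39% to 47% on average. To hold the rate at 5% per dataset, the multiplier would have to be about 5.3, 4.7 and 4.4 SD instead of 3. The contradiction between the preamble and step 2e, and the missing with/without reporting, are plain from the text and need no assumption.

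The reach is limited to the secondary descriptive PK summaries; the primary excretion endpoint is untouched. How often the rule would act cannot be known from the documents, because they give neither a trigger nor a CV. This should be corrected, but it does not threaten the study's main result.

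**What to change.** In the n ≥ 6 branch of SAP 9.3.1, require what the n < 6 branch already requires: results with and without the atypical value, both reported, at every n this study can reach. Name the all-subject summary as the main result, and allow outright exclusion only for a documented dosing, sampling or assay error. These last two points go slightly beyond the present n < 6 text, but without them the SAP would not say which summary to rely on.

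Reword step 2e to agree with the preamble, for example: *may be flagged as an outlier; results are reported with and without it*.

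The cost is a few lines of SAP text and one extra summary whenever a value is queried. Reported CVs may be larger than under the present rule.
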